2.0 Known safety experience with ivacaftor

Up to now, more than 25 studies of ivacaftor have been completed or are ongoing in more than 400 healthy adult subjects and 680 adult and pediatric subjects with CF.

In completed studies in subjects with CF the most common adverse events reported in subjects receiving ivacaftor were Cough (34%) CF Pulmonary exacerbation (29%) Headache (17%) Upper respiratory tract infection (16%), Nasal congestion (16%), Oropharyngeal pain (mouth and throat pain) (15%), Pyrexia (fever) (11%), Productive cough (10%), Nausea (10%), Rash (10%), and Dizziness (5%).

A few subjects with CF receiving ivacaftor as well as placebo have shown signs of liver injury. In these cases, the liver injury was noticed as abnormalities in blood tests which were monitored as part of the study. The very high levels of these tests, called ALT and AST, led to stopping of Study Drug, although in some cases this was placebo. The levels of ALT and AST improved after Study Drug was stopped. Very severe cases of liver injury can become permanent or be life-threatening, although this has not been observed with ivacaftor. Overall, the data does not support an association between ivacaftor and ALT and AST elevations.

In programs that were designed to provide access to ivacaftor for subjects with CF and life-threatening severe lung disease, four deaths were reported. In a long term, open-label

extension study of ivacaftor in subjects with CF, two deaths were reported. The deaths were not considered related to ivacaftor.

The Study Drug may contain a very small amount of lactose, a sugar found in dairy products. The amount of lactose in a single pill is roughly the same as the amount in one teaspoon of milk. This amount of lactose is unlikely to cause symptoms in people who have lactose-intolerance.

3.0 Reproductive Risk related to ivacaftor:

The effects of ivacaftor on the reproductive system (sperm, eggs) or the unborn child are not known and may be hazardous. Birth defects, including physical deformities, mental retardation, and other problems, as well as premature birth are known risks of some drugs. For this reason, people taking ivacaftor should not become pregnant or father a child (or donate sperm). Women should not breastfeed a baby while in this study.

3.1 Possible Risks of Ivacaftor Based on Animal Studies:

In a study in which ivacaftor was given to newborn rats, cataracts (cloudiness of the lens of the eye) were seen. No cataracts were seen in studies of older animals (rats and dogs) dosed with ivacaftor for longer periods of time. No cataracts associated with ivacaftor use have been reported in humans in any ivacaftor studies to date. The significance of this finding to humans is not known. It is presently thought to only be a concern for very young individuals taking ivacaftor.

4.0 STUDY DESIGN

The study is a Phase 2 Study to establish the safety and efficacy of the CFTR potentiator ivacaftor in patients with chronic obstructive pulmonary disease (COPD), chronic bronchitis, and acquired CFTR dysfunction as detected by sweat chloride analysis. The design is a pilot, randomized (3:1, active:placebo), double-blind, placebo-controlled study to determine the safety and efficacy of ivacaftor (VX-770) in approximately 40 subjects with COPD.

Enrollment is planned at our single center, The University of Alabama at Birmingham. Patients will be randomized 3:1 to active drug (n=30) and placebo (10) to achieve the enrollment goal.

- A sufficient number of subjects will be screened to randomize up to 50 subjects to achieve 40 completed subjects to receive either ivacaftor 150 mg BID (n=30) or placebo (n=10) for 84 days.
- The schedule of assessments is shown in Table 1. The protocol design is shown in Figure 1.
- Ivacaftor and matching placebo will be orally administered as capsules according to the following guidelines:
 - Between study visit Day 1 and study visit Day 84, subjects will take 1 dose of study drug each day in the morning, beginning any time between 08:00 h (8:00 AM) and 12:00 h (12:00 PM). Whenever possible, subjects should take the study drug at the same time each day.

- On the study visit days when PK samples are collected (study visit Days 1, 28, 56, and 84), the study drug is to be taken by the subject while he/she is at the study site
- For visits after the Day 1 visit, subjects will be instructed to bring all remaining study drug materials to the site; study drug will be dispensed at each visit.
- Ivacaftor will be prepared and dispensed by an unblinded pharmacist.
- Subjects will be instructed to continue their standard COPD medication regimen.

Table 1. Schedule of Assessments ^a8 hr PK (pre, 1, 2, 4, 8, hr samples). ^b peak and trough PK only, ^crandom PK, ^donly if indicated.

Assessment	Screen (Day -28 to -1) Visit 1	Day 1	Day 28 (± 2)	Day 56 (± 2)	Day 84 (± 2)	Follow Up (Day 98 ± 2)
		Visit 2	Visit 3	Visit 4	Visit 5	Visit 6
Informed Consent	X					
Medical History & Concomitant Medications	X	X	X	X	X	X
Physical Examination	X	X	X	X	X	X
Safety Labs	X		X	X	X	X ^d
CFTR Genotyping	X					
Urine Pregnancy Test		X	X	X	X	X
Serum Pregnancy Test	X					
Blood Biomarker Collection		X	X	X	X	X
Spirometry	X	X	X	X	X	X
Sweat Chloride	X	X	X	X	X	X
MCC	X				X	
Patient report outcome questionnaires		X	X	X	X	X
Pharmacokinetics		X ^a	X ^b	X ^c	X ^b	X
Drug Administration		X	X	X		
Drug Dispensing & Drug Return		X	X	X		
Ocular exam	X					
6 minute Walk test		X			X	

4.1 Safety Assessments:

All other blood samples for laboratory assessments will be collected at the times specified in the table. All blood samples will be collected while subjects are in a seated or supine position and will be analyzed at the UAB Outreach Laboratory (a CLIA and Clinical Research Certified Laboratory).

The clinical laboratory test panels will include the following:

Hematology:

- Hemoglobin
- Hematocrit

- Red blood cell (RBC) count
- Platelet count
- White blood cell (WBC) count
- Differential (absolute and percent)
 - Eosinophils
 - Basophils
 - Neutrophils
 - Lymphocytes
 - Monocytes

Serum Chemistry:

- Glucose
- Blood urea nitrogen (BUN)
- Creatinine
- Sodium
- Potassium
- Calcium
- Inorganic phosphate
- Total bilirubin
- Alkaline phosphatase
- Serum aspartate transaminase (AST)
- Serum alanine transaminase (ALT)
- Lactate dehydrogenase (LDH)
- Gamma-glutamyl transpeptidase (GGT)
- Total protein
- Albumin
- Indirect bilirubin
- Hemoglobin A1c
- Amylase
- Lipase

Urine Pregnancy test (for females only)

Coagulation studies:

- Prothrombin time (PT)
- Activated partial thromboplastin time (aPTT)
- PT International Normalized Ratio (PT INR)

4.2 Other Assessments:

CFTR genotyping (for eligibility evaluation). Commercially available CFTR genotype analysis that includes 49 mutations including the 23 recommended by the ACGME and reflex testing for the intron 7 polythymidine sequence (e.g. 5T variant analysis). Depending on results and funding, we may also perform CFTR sequencing to evaluate for less common CFTR variants.

Pharmacokinetic levels of ivacaftor: Serum ivacaftor levels will be measured by gas chromatography/MS/MS on human serum, using a protocol established at UAB. Evaluation will be conducted at the times listed in Table 4-1. PK levels will be evaluated at the planned interim analysis (see below) and upon completion of the study.

Ocular exam: Ocular exam to assess for the presence of cataracts will be performed during screening window for patients without a known prior history of cataracts or an ocular exam within the last year prior to screening.

Serum biomarker collection

Routine biomarker collection facilitated by the UAB Pulmonary Biorepository will be held for long-term storage for future analysis:

- Buffy coat
- Plasma
- Serum

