- Uncontrolled Diabetes
- Recent (e.g 1year) arterial thrombotic events (peripheral arterial disease, thrombotic stroke)
- Clinically significant arrhythmias requiring anti-arrhythmic agent(s) or conduction abnormalities that in the opinion of the investigator that affect patient safety such as the abnormalities listed below (patients with stable coronary artery disease are eligible)
 - ♦ Angina symptoms
 - ♦ History of MI
 - ♦ Revascularization procedure in the last year prior to screening
 - ♦ Clinically significant congestive heart failure (known LVEF $\leq 45\%$, cor pulmonale, diastolic heart failure, etc)

Investigational Drug: Ivacaftor, 150 mg PO every 12 hrs (or matching placebo)

Schedule of Study Visits: The first dose of ivacaftor will be administered at the Day 1 visit. Ivacaftor will be taken twice daily, with 12 hours between each dose from day 1 through the morning dose of day 84. Study visits will occur at Screening (-28 to -1 days), Day 1, Day 28 (\pm 7), Day 56 (\pm 7), Day 84 (\pm 7), and Follow-up (14 \pm 7 days after the last dose of ivacaftor).

Outcome Measures:

Safety assessments: Assessments include tests used in clinical studies to monitor the safety of ivacaftor in CF, including adverse event reporting, clinical laboratory testing, physical exams, and spirometry. The PI will review all SAEs in real time and conduct appropriate reporting to the FDA and IRB, as required, within 24hrs at maximum. Interim safety analysis will include review of AEs and safety labs by the PI and will be conducted after completion of approximately 10, 20, and 30 subjects. Ocular exam will be performed at baseline unless known history of cataracts.

PK: PK/PD analyses between ivacaftor levels and CFTR activity in the sweat gland will reveal new insights into the degree that wild-type CFTR can be activated. Calculated PK parameters include: area-under-the-curve (AUC₁₂), maximum plasma concentration (C_{max}), time to C_{max} (T_{max}), oral clearance (CL/F), terminal apparent distribution volume (V_z/F), and elimination half-life (t_{1/2}). Subsequently, intensive data and sparse plasma concentrations will be combined to create a population PK model to assess covariates, such as age, weight, sex, smoking status, etc. as previously conducted by our group for NIH and industry sponsored studies.

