9.0 Study Drug Administration and Management

Ivacaftor should be administered every 12 hours. It is recommended that subjects take ivacaftor approximately 30 minutes after the start of a meal or snack. Whenever possible subjects should take ivacaftor at the same time each day. On day 1 subjects who meet all inclusion and exclusion criteria will be enrolled in the study. In this study, all subjects will receive 150 mg ivacaftor BID or placebo. The research pharmacist will provide logs of investigation product and maintain those in a study binder.

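### Section 4.0 tells subjects to take one dose each morning, against 150 mg every 12 hours everywhere else; the synopsis visit windows also conflict with Table 1 and outrun the drug supply

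*Combined protocol and SAP*

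**What the plan says.** **Dose.** In Section 4.0, the guideline for the period from the Day 1 visit to the Day 84 visit is that "subjects will take 1 dose of study drug each day in the morning", starting between 08:00 and 12:00. Five statements give a different regimen:

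- Synopsis, Investigational Drug: 150 mg by mouth at 12-hour intervals.
- Synopsis, Schedule of Study Visits: "Ivacaftor will be taken twice daily, with 12 hours between each dose from day 1 through the morning dose of day 84".
- Section 4.0, an earlier bullet: subjects are to "receive either ivacaftor 150 mg BID (n=30) or placebo (n=10) for 84 days".
- Section 9.0: "Ivacaftor should be administered every 12 hours".
- Section 9.0 again: "all subjects will receive 150 mg ivacaftor BID or placebo".

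**Windows.** The synopsis sentence beginning "Study visits will occur at Screening (-28 to -1 days), Day 1, Day 28" attaches ±7 days to Days 28, 56 and 84, and sets follow-up at 14 ±7 days after the last dose. Table 1 gives ±2 days for the same three visits and for follow-up on Day 98. No text says which governs.

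**Supply.** Section 11.0 dispenses 28 days (±2) of drug on Day 1 and a further 28 days at Days 28 and 56, with all drug returned at Day 84. Section 10.0 gives the tablet strength as 150 mg.

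**The concern.** The Section 4.0 sentence is a practical instruction on daily intake, and it halves the dose. Anyone drafting subject instructions or judging compliance from that list could cite the wrong regimen. The sampling is also affected: Table 1 schedules "peak and trough PK only" at Days 28 and 84, and a trough after once-daily dosing is a different quantity from a 12-hour trough. The planned AUC over 12 hours (synopsis and Section 20.0) likewise presupposes a 12-hour interval.

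The window conflict matters because drug is dispensed only at visits. If the synopsis windows were used, a late visit could come after the drug had run out. Day 84 is the only post-baseline MCC measurement in Table 1. FEV1, sweat chloride and PK are also measured then, and the off-drug comparison in Section 6.0 assumes that subjects are still on drug at that visit.

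**Working it through.** **1. Dose.** Doses at twice daily from the morning of Day 1 through the morning of Day v: N(v) = 2(v − 1) + 1.

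- Intended regimen: N(84) = 2 × 83 + 1 = 167 doses, or 167 × 150 = 25,050 mg.
- Section 4.0 sentence: one dose on each of 84 days = 84 doses, or 84 × 150 = 12,600 mg.
- Ratio: 84/167 = 0.50.

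**2. The plan's own supply, visits on time.** Three 28-day supplies give 3 × 28 × 2 = 168 tablets against 167 needed. The stated supply works when visits are on schedule.

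**3. Late visits, with leftovers carried over.** The ±2 days in Section 11.0 is read as 28 to 30 days for the first supply.

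| Visit on | Needed, N(v) | Supplied 28/28/28 | Supplied 30/28/28 |
|---|---|---|---|
| Day 30 (+2) | 59 | 56: 3 short | 60: 1 spare |
| Day 58 (+2) | 115 | 112: 3 short | 116: 1 spare |
| Day 86 (+2) | 171 | 168: 3 short | 172: 1 spare |
| Day 35 (+7) | 69 | 56: 13 short | 60: 9 short |
| Day 63 (+7) | 125 | 112: 13 short | 116: 9 short |
| Day 91 (+7) | 181 | 168: 13 short | 172: 9 short |

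The +2 windows are covered if the first supply is 30 days. The +7 windows are not covered in either case.

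**4. Gap before a Day 35 visit.** 34 full days precede the visit and 28 to 30 are supplied: 34 − 30 = 4 to 34 − 28 = 6 days without drug. Carry-over is irrelevant here, as this is the first interval.

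**5. Gap before a Day 91 visit, if dosing continues to the visit.** The table gives the total shortfall but not when it falls. The total is 6 days plus the Day 91 morning dose (13 doses), or 4 days plus that dose (9 doses). Days lost before an earlier late visit are not lost again later.

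- Visits on Days 28, 56, 91: drug runs out after Day 84 or Day 86, so the gap is Days 85–90 (6 days) or Days 87–90 (4 days).
- Visits on Days 35, 63, 91 or 35, 56, 91: the gap falls before Day 35. From Day 35 the subject is continuously on drug and lacks only the Day 91 morning dose.
- Visits on Days 28, 63, 91: the gap falls before Day 63. Again only the Day 91 morning dose is missing.

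**6. If dosing stops on calendar Day 84,** as the synopsis sentence reads, 167 doses are needed against at least 168 supplied, so there is no final shortfall. A Day 91 visit is then 91 − 84 = 7 days after the last dose for that reason instead.

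**The case against.** The strongest reply is that nobody would be misled. Five statements say twice daily. Section 9.0, the section on study drug administration, also covers meals and time of day. The trial is at a single centre, with a pharmacist dispensing. This stands as to likelihood: a reader might infer that subjects will be half-dosed or that the PK endpoint is compromised, and the documents do not support that. It does not make the sentence correct.

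A second reply is that Table 1 and Section 11.0 agree on ±2, so the shortage arises only by pairing the synopsis window with another section's supply. That also stands. The synopsis is the outlier, and the remedy is to correct it.

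Two stronger readings should be resisted. A reader might infer that every late final visit is 4 to 6 days off drug. That needs earlier visits on time or early and dosing that continues beyond the synopsis's Day 84 end. A reader might also infer that supply fails even within Table 1's window, because returned drug is retained at the site: from an on-time Day 56 visit to Day 86, 2 × 30 = 60 doses are needed against 56, so 4 short. That rests on a Table 1 row that combines dispensing with return and is also marked on Day 1, when nothing can be returned, and on a Section 12.0 sentence that gives no timing. Section 11.0 places the return of all drug at Day 84, which favours carry-over.

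**Conclusion.** The Section 4.0 dosing sentence is wrong by a factor of two and must be corrected: 150 against 300 mg/day, and troughs at about 24 instead of 12 hours. The case for correcting it rests on the text itself; actual once-daily dosing is not expected.

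The window conflict is real but secondary. Under +7, a Day 35 visit follows 4 to 6 days without drug. A Day 91 visit follows 4 to 6 days without drug only under the conditions in steps 5 and 6; if dosing ends on calendar Day 84, the Day 91 measurements are about 7 days off drug anyway. Early visits are unaffected.

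The assumptions are full adherence until supply runs out, a first dose on the morning of Day 1, one 150 mg tablet per dose, and the 28-to-30-day reading of Section 11.0. Reading its tolerance downwards would enlarge the gaps; applying 30 days to all three dispensings would leave 180 tablets against 181 at Day 91. None of the power or alpha figures in Section 6 depends on any of this.

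**What to change.** 1. Replace the Section 4.0 sentence with: 150 mg every 12 hours (one morning and one evening dose); on PK visit days the morning dose is taken on site.
2. Change the synopsis windows for Days 28, 56 and 84, and for follow-up, to the ±2 days of Table 1. State that dosing runs through the morning of the Day 84 visit, whatever calendar day in the window that is.
3. In Section 11.0, specify 30 days on Day 1, then 28 and 28 days, with unused drug counted and given back to the subject until the Day 84 visit. This covers every +2 visit with one dose to spare; it makes no allowance for lost tablets.
4. Housekeeping: in Section 12.0, limit retention at the site to used materials and to drug returned at Day 84 or early termination. In Table 1, mark Drug Administration and Drug Return at Day 84.

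The cost is wording changes and two table marks. The 30-day first supply adds 60 − 56 = 4 tablets per subject, already within the Section 11.0 tolerance. No visits or procedures are added.

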16.8 Elevation of Liver Function Test Parameters

Subjects with new ALT or AST elevations of $>3 \times$ ULN and clinical symptoms be followed closely, including repeat confirmatory testing within 48 to 72 hours of the initial finding and subsequent close monitoring of ALT and AST level, as clinically indicated.

Study drug administration will be interrupted immediately and the DSMB Chair will be notified if any of the following criteria is met:

- ALT or AST $>8 \times$ ULN
- ALT or AST $>5 \times$ ULN for more than 2 weeks
- Total bilirubin $>2 \times$ ULN and/or clinical jaundice, in association with elevation of ALT or AST $>3 \times$ ULN

A thorough investigation of potential causes should be conducted and the subject will be followed closely for clinical progression.

If no convincing alternative etiology (e.g., viral hepatitis, alcohol ingestion) for the elevated transaminases is identified, regardless of whether ALT or AST levels have improved, the subject will be discontinued from the study, in consultation with the Medical Monitor

An early termination visit should be scheduled as soon as possible. In addition to the early termination visit assessments specified in the protocol, a blood sample should be obtained for pharmacokinetic analysis. Subjects discontinued for elevated transaminases should be followed until their transaminases normalize or return to baseline. If a convincing alternative etiology for the elevated transaminases is identified and the subject's symptoms and laboratory findings have improved, the investigator will consider resuming study drug treatment in consultation with the PI.

16.9 Definition of COPD Exacerbation.

We will monitor the incidence and severity of COPD exacerbations to measure safety of ivacaftor and estimate whether a reduction in COPD exacerbations is plausible with effective CFTR potentiation by ivacaftor, and to develop sample size estimates for future studies. For the purposes of this protocol, COPD exacerbations will be defined as follows: a complex of respiratory symptoms (increase or new onset) of more than one of the following: cough, sputum, wheezing, dyspnea, or chest tightness, requiring treatment with antibiotics and/or systemic steroids for at least three days.

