18.0 Interim Analysis

18.1 Interim Safety Analysis

Interim safety analysis will include blinded review of AEs, ECGs, and safety labs by the PI and will be conducted after completion of 10, 20, and 30 subjects. The interim safety analysis will include an interim safety report prepared by the PI for all Co-Investigators to review. This report will include a summary of the following:

- Demographics and baseline characteristics
- Enrollment
- Adverse events
- Withdrawals
- Exacerbation and hospitalization rates

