18.3 Interim Efficacy Analysis

No interim efficacy analyses are planned for the study.

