20.0 PK and PK/PD Analysis

Intensive PK Analysis will be conducted at UAB by Dr. [name]'s laboratory using LC/MS/MS method already established at our laboratory and described in the pilot study.¹² Calculated PK parameters include: area-under-the-curve (AUC₁₂), maximum plasma concentration (C_{max}), time to C_{max} (T_{max}), oral clearance (CL/F), terminal apparent distribution volume (V_z/F), and elimination half-life (t_{1/2}). Subsequently, intensive data and sparse plasma concentrations will be combined to create a population PK model to assess covariates, such as age, weight, sex, smoking status, etc. as previously conducted by our group for NIH and industry sponsored studies. PK/PD analyses between ivacaftor levels and CFTR activity in the sweat gland will reveal new insights into the degree that wild-type CFTR can be activated by the CFTR potentiator ivacaftor.

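### Does the PK evaluation that Section 4.2 ties to an interim analysis put the blind at risk?

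*Combined protocol and SAP*

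**What the plan says.** Section 4.2 (Other Assessments) has a short paragraph on ivacaftor levels, which schedules their evaluation: "PK levels will be evaluated at the planned interim analysis (see below) and upon completion of the study".

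The interim is described in three places. The Synopsis, under safety assessments, lists AEs and safety labs. Section 17.0 gives the timing: when 10, 20 and 30 subjects have completed 84 days. Section 18.1 gives the content: "Interim safety analysis will include blinded review of AEs, ECGs, and safety labs by the PI". It adds a report to the Co-Investigators on baseline data, accrual, AEs, withdrawals, and exacerbation and hospital admission rates. PK is in none of these lists. Section 18.3 says "No interim efficacy analyses are planned for the study". The numbering runs from 18.1 to 18.3.

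Section 14.0 names the pharmacist as unblinded and lets the PI be unblinded only when an event requires it. Section 16.8 asks that, for a subject stopped for raised transaminases, "a blood sample should be obtained for pharmacokinetic analysis".

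The same paragraph of Section 4.2 also states "Serum ivacaftor levels will be measured by gas chromatography/MS/MS on human serum" and "Evaluation will be conducted at the times listed in Table 4-1". Section 20.0 has the PK work done at the center "using LC/MS/MS method already established at our laboratory", and both it and the Synopsis refer to plasma concentrations. Section 4.0 says "The schedule of assessments is shown in Table 1".

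**The concern.** Two things look wrong at first.

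The first is the blind. Placebo subjects should have no measurable ivacaftor, so a list of levels by subject is close to a list of allocations. If such a list were part of an interim that the PI conducts and reports to all Co-Investigators, the PI's review would no longer be blind for those subjects. Relatedness calls still open (Sections 16.3 and 17.0) and follow-up assessments still to come, which Section 6.0 uses for the off-drug effect, would then be made with knowledge of the arm. Safety is a primary endpoint and rests partly on those calls. The sample in Section 16.8 raises the same question for one subject at a time, while a liver event is still being followed.

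The second is consistency. PK is also a primary endpoint, yet the paragraph that describes its measurement disagrees with Section 20.0 on assay and with Section 20.0 and the Synopsis on matrix. It cites a table number that is not the schedule's, and it speaks of one interim where Section 18.1 has three looks.

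**Working it through.** The plan states no sample size, power or alpha figure on this point, so the check compares the sections.

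**Step 1. Which interim is meant?** Section 18.3 excludes an efficacy interim, so the safety interim is the only one described. Both contents statements in Section 18.1 use the verb include, so the lists are not exclusive. The pointer in Section 4.2 may also aim at a Section 18.2 that is missing from the available text. The cross-reference is unresolved, but it contradicts nothing.

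**Step 2. Which ways of carrying out Section 4.2 fit the rest of the plan?**

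| Way of doing it | 4.2 (PK evaluated at an interim) | 18.1 (PI review blinded) | 14.0 (PI unblinded only for an event) |
|---|---|---|---|
| Laboratory evaluates levels and keeps subject-level results | met | met | met |
| Subject-level levels go to the PI or Co-Investigators at the interim | met | breached | breached |

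Section 4.2 requires that levels be evaluated. It does not require that they be reported to anyone. Section 20.0 already places the analysis with the PK laboratory. Of the two ways, only the first satisfies all the provisions, so a team following the plan has to take it.

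**Step 3. The Section 16.8 sample.** The text asks for a sample to be drawn. It sets no immediate assay and no return of the result to the investigator. The only timing stated anywhere for evaluating levels is that in Section 4.2.

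**Step 4. What would be exposed if the second way were followed?** With 3:1 allocation, a look at n completers holds on average 0.75n active and 0.25n placebo subjects:

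- n = 10: 7.5 and 2.5
- n = 20: 15 and 5
- n = 30: 22.5 and 7.5

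These counts only restate the milestones. They do not measure an effect of the plan, because no section provides for such a release. Even then, the completers reviewed would have passed Day 84, where Section 6.0 takes the pharmacodynamic change. By Table 1, MCC and the 6-minute walk are not done at follow-up. That leaves the off-drug comparison and any late causality calls.

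**Step 5. Type I error.** Section 6.0 attaches no hypothesis test to PK, and Section 18.3 rules out an interim look at efficacy. An interim evaluation of levels spends no alpha.

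**Step 6. The drafting mismatches.**

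| Item | Section 4.2 | Elsewhere |
|---|---|---|
| Assay | gas chromatography/MS/MS | LC/MS/MS (20.0) |
| Matrix | serum | plasma (Synopsis, 20.0) |
| Schedule | Table 4-1 | Table 1 (4.0) |
| Interim | one | looks at 10, 20 and 30 completers (18.1) |

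Table 1 stands in Section 4 and gives the PK visits, with the Day 1 sampling hours in its caption, so the table number is a clerical slip. The assay and matrix wording does not enter the sample size, the tests or the list of PK parameters. Section 20.0, the dedicated PK section, points to a method already running in the laboratory and described in the pilot study. No result has been shown to change with either wording.

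**The case for a change.** The strongest case is that silence is not a safeguard. The trial is run at a single center, and Section 20.0 describes the assay laboratory as the team's own, so levels are produced close to the people who must stay blind. Section 14.0 does not mention PK results. Study drug is taken at the site on PK visit days, so an undetectable post-dose level would be informative too. Section 4.2 does not limit the interim evaluation to completers, so subjects still on treatment could be included and more than the follow-up visit would be affected. One or two sentences would remove the doubt.

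Part of this stands. A written rule on who receives concentrations is good practice, and the paragraph in Section 4.2 is worth tidying when the text is next edited.

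The rest does not carry the point further. The objection needs levels to reach the investigators, and no section sends them there. The general provisions on blinding apply to PK results as they do to any other data that reveal the arm, so the absence of a PK-specific rule does not permit release. The argument from Section 16.8 assumes that a result comes back while the liver event is being followed, which the text does not say. A blanket embargo would also bear on how a suspected liver event is handled, so it is not free of cost. The assay, matrix and table mismatches have no bearing on who sees the levels.

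**Conclusion.** The concern does not hold as a fault in the plan. Section 4.2 leaves open which look, if any, carries the PK evaluation and who receives its output. That is a gap in detail which the existing blinding provisions fill in only one acceptable way: subject-level levels stay outside the blinded team. On that reading the effect on the blind, the type I error and the estimates is zero.

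The assay, matrix, table-number and interim-count mismatches are real but editorial.

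The conclusion rests on two assumptions: that the team honors the blinded review in Section 18.1 and the event-only unblinding in Section 14.0, and that one assay and one matrix are used for all PK samples. Nothing in the documents points the other way on blinding. The assay wording differs between sections, but nothing suggests that two methods are to be used side by side.
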